5.0 STUDY PROCEDURES

5.1 Screening/Baseline Procedures (60-0 days before surgery)

Assessments performed exclusively to determine eligibility for this study will be done only after obtaining informed consent. Assessments performed for clinical indications (not exclusively to determine study eligibility) may be used for baseline values even if the studies were done before informed consent was obtained.

All screening procedures must be performed prior to registration unless otherwise stated. The screening procedures include:

5.1.1 Informed Consent

5.1.2 Medical history

Complete medical and surgical history, history of infections

5.1.3 Demographics

Age, gender, race, ethnicity

5.1.4 Review subject eligibility criteria

5.1.5 Review previous and concomitant medications

5.1.6 Physical exam including vital signs, height and weight

Vital signs (temperature, pulse, respirations, blood pressure), height, weight

5.1.7 Performance status

Performance status evaluated prior to study entry according to Appendix A.

5.1.8 Adverse event assessment

Baseline adverse events will be assessed. See section 6 for Adverse Event monitoring and reporting.

5.1.9 Hematology

Complete Blood Count (CBC) to include: white blood cells (WBC), red blood cells (RBC), hemoglobin (HGB), hematocrit (HCT), MCV, MCHC, WBC differential, platelet count.

5.1.10 Serum chemistries

Comprehensive metabolic panel (CMP) to include: albumin, alkaline phosphatase, ALT/SGPT, AST/SGOT, BUN, creatinine, electrolytes (sodium, potassium, calcium, chloride, bicarbonate), glucose, and total bilirubin.

5.1.11 Pregnancy test (for females of child bearing potential)

Will be performed prior to 5-ALA administration preoperatively as standard operating procedure for all surgical patients.

5.1.12 Tumor assessment

Standard of care pre-operative imaging will be conducted as part of usual surgical planning.

5.2 Procedures During Treatment

5.2.1 Day 0 (Day of Surgery) 5-ALA Administration

- · Physical exam, vital signs
- Administration of 5-ALA 3h prior to surgery- single dose oral 20mg/kg
- · Monitoring for adverse events

5.2.2 Day 0 (Day of Surgery) Fluorescence-Guided Surgery

- Intraoperatively, blue light microscopy will be used to visualize tumor.
- Images will be captured during resection, and surgeon will assign subjective fluorescence scores of no brightness (0), mild brightness (1-pink), moderate brightness (2-orange) or robust brightness (3- lava-like orange). Fluorescence homogeneity or heterogeneity will be noted. After excision the tumor will again undergo imaging to characterize 5-ALA fluorescence and homogeneity or heterogeneity.
- Patient vital signs will be monitored and recorded throughout surgery.
- Following pathology analysis, tumor classification will be recorded.
 Histopathologic examination of tumor specimens will be correlated with
 fluorescence on intraoperative imaging. Morphological factors such as tissue
 cellularity, cytological atypia, nuclear hyperchromasia, as well as tumor
 markers and immunostaining will be examined. Presence of positive or
 negative surgical margins will be recorded.
- 5-ALA sensitivity, specificity, positive predictive value and negative predictive value will be determined for different tumor types and histopathology based on correlation of intraoperative fluorescence with tumor pathology.

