2.3 Endpoints

2.3.1 Definition:

Safety: Gleolan®-related adverse events will be recorded using standardized toxicity criteria and known side effect profile up to 6 weeks after surgery. Monitoring for adverse events will take place before and after Gleolan® administration, 48h after surgery, 2 weeks and 6 weeks postoperatively.

2.3.1 Primary endpoint:

The feasibility of using oral Gleolan® as an adjunct diagnostic imaging tool for malignant tumor tissue fluorescence will be primarily assessed by computing sensitivity of intraoperative Gleolan® induced PPIX tissue fluorescence.

PPIX tissue fluorescence will be defined categorically as "no" (score 0), "low" (score 1), "medium" (score 2), and "high" (score 3) by operative surgeon, and images will be recorded. For purposes of computing measures of diagnostic performance a score of 0 will be considered a negative test result and a score of 1, 2 or 3 will be considered a positive test result.

2.3.2 Secondary endpoints:

2.3.2.1 The diagnostic performance of Gleolan® will further be assessed by computing measures of specificity, positive predictive value (PPV), negative predictive value (NPV), and accuracy of intraoperative Gleolan® induced fluorescence with a score of 0 will be considered a negative test result and a score of 1, 2 or 3 will be considered a positive test result.

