Photographs will be taken during the 'blue light' imaging to provide identification of optical fluorescent tumor. Images will be taken before, during and after resection to capture tumor fluorescence. All tumor specimens will be sent to pathology for frozen examination as per institutional standard of care. Any tissue specimens from the fluorescent areas will be photographed and sent for permanent histopathologic examination and molecular genetic analysis to confirm the presence of malignant tumor. The intraoperative pictures of the resection cavity in the 'blue light' mode will be analyzed to provide confirmation of tissue/tumor fluorescence associated with tumor resection. The surgeon will document whether visualization of fluorescence was present with each of the labeled tissue specimens. The remainder of the resection will be performed with the ability to switch between white light and blue light as chose by the surgeon. If no fluorescence is observed in the resection site it will be noted, but will otherwise undergo identical tumor resection, photography and histopathologic examination.

Pathologic confirmation of tumor type will be made by a pathologist who will not be informed of the fluorescence status of the tissue samples. Histopathology will characterize the resected tissue as

- (1) Diagnostic tissue or not
- (2) Presence of malignant tumor cells
- (3) Pathologic grading and tumor type

Genetic testing will be performed in accordance with standard of care at the testing institution for the tumor specimens.

4.5 **Duration of Therapy**

One-time, single dose administration of oral Gleolan®(5-ALA) (20mg/kg) is planned 3-5h prior to induction of anesthesia. However, surgery can be initiated up to 8 hours after dosing. In the event of allergic reaction, other severe adverse effect, or changes in the patient's condition prior to surgery rendering the patient unacceptable for further treatment in the judgement of the investigator, or patient decides to withdraw from the study, the therapy protocol will be ended and fluorescent-guided surgery will not proceed.

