8.2 Sample Size and Accrual

There is no previous publication for applying 5-ALA to head and neck cancer patients. The sample size calculation is based on the experience of 5-ALA in brain cancer. A literature review study summarized the usage of 5-ALA in patients with malignant Gliomas between 2000 and 2015.3 The sample sizes in the studies included in the review ranged from 11 to 97. The sensitivity ranged from 75% and 95% while the specificity ranged from 53% to 96%. In our study, all tissue samples will be collected from the head and neck cancer patients undergoing standard of care surgical resection. The surgeons will provide the pathologists with the patient resected specimen marked, typically in 4 different regions with 3 regions located within the tumor region and 1 located at the boundary or outer region of the tumor. Each region will be marked according to the associated intensity of the PPIX tissue fluorescence score at that location as no brightness (0), mild brightness (1-pink), moderate brightness (2-orange) or robust brightness (3- lava-like orange). Thus each patient is expected to contribute 1 tissue sample from a normal margin region and 3 tissue samples from the tumor tissue region at a ratio of 1:3 (i.e. the pathologists will examine the samples from each patient histopathologically), which translates to a tumor tissue prevalence of 75% in the overall tissue samples.

The following calculations were performed using PASS 15 Power Analysis and Sample Size Software (2015). NCSS, LLC. Kaysville, Utah, USA, ncss.com/software/pass and using the methods for calculating sample size for co-primary endpoints of sensitivity and specificity.⁴¹⁻⁴³

Assuming a prevalence of 75% and a sample sensitivity of 85%, the sample size needed to estimate a two-sided 95% sensitivity confidence interval with a width of at most 35% (\pm 17.5% precision assuming asymptotic with continuity correction method) is at least 23.We will use a sample size of 23 in this study.

If the prevalence is as low as 50% in our sample then the width of our 75% sensitivity confidence interval will increase to 40.6% (± 20.3 precision) which still gives a lower bound for the CI above 50%.

The sample size calculation is performed conservatively assuming only 1 measure per patient, but there will be typically 4 per patient which will improve precision of estimates.

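### The surgeon picks the verified spots with the fluorescence in view and also scores them, so sensitivity is likely to be biased upward and specificity in either direction; the masking text also conflicts

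*Combined protocol and SAP*

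**What the plan says.** Sections 2.3 and 5.2.2 make the operating surgeon the reader of the index test: the "surgeon will assign subjective fluorescence scores of no brightness (0), mild brightness (1-pink" and so on up to 3. Colour words are the only criteria. Sections 2.3 and 8.3 call a score of 0 negative and 1, 2 or 3 positive. Sensitivity is the primary endpoint; specificity, PPV and NPV are secondary.

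The same surgeons choose what is verified. Section 8.2 states: "The surgeons will provide the pathologists with the patient resected specimen marked, typically in 4 different regions". Three of these are to lie inside the tumor and one at its edge or outer part. On labelling, the section says: "Each region will be marked according to the associated intensity of the PPIX tissue fluorescence score at that location".

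Section 4.4 describes resection continuing in blue-light mode after standard entry, with switching between white and blue light as the surgeon chooses. It adds: "Any tissue specimens from the fluorescent areas will be photographed and sent for permanent histopathologic examination". Two safeguards appear there. Where nothing fluoresces: "If no fluorescence is observed in the resection site it will be noted, but will otherwise undergo identical tumor resection", with the same photography and histology. And tumor type is confirmed by "a pathologist who will not be informed of the fluorescence status of the tissue samples".

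Images are recorded and are to be analyzed, but the endpoint rests on the surgeon's score. No second reader, and no rule for placing a region within its zone, is described.

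**The concern.** A sensitivity estimate is unbiased only if the verified tumor spots represent tumor tissue with respect to fluorescence. Here the person placing the mark has already seen which spots are bright, and the plan constrains the zone but not the spot. That person also knows the tumor location when making the 0-versus-1 call that decides positivity.

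The study is single-arm, so no comparator would reveal a bias. The four samples per patient that section 8.2 counts on for better precision would only narrow the interval around a shifted value.

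The second issue concerns the reference standard. If the marks on the specimen convey the score, the pathologist is not masked. Section 8.3 places the malignant/benign line between moderate and light dysplasia, a judgement that a known score could sway.

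**Working it through.** **1. The plan's own figure.** Inputs from section 8.2: sensitivity p = 0.85, prevalence 0.75, 95% interval of width at most 35%, asymptotic method with continuity correction. The half-width is 1.96·√(p(1−p)/n) + 1/(2n). At n = 17 tumor samples it is 0.170 + 0.029 = 0.199, giving an interval from 0.651 to 1 (upper limit cut at 1) and a width of 34.9%. Then 17/0.75 = 22.7, so N = 23, which matches. At 50% prevalence (n = 11) the width is 40.65%, against the stated 40.6%. The sample size stands; the point here is bias, not precision.

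**2. Effect of choosing the spot by brightness (assumed rule).** Suppose each tumor spot is positive with probability 0.85, two candidate spots have correlation ρ, and the brighter is always marked. Then

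P(marked spot positive) = 1 − [0.15² + ρ·0.85·0.15]

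| ρ | Apparent sensitivity | Excess over 85% (points) |
|---|---|---|
| 0 | 97.8% | 12.8 |
| 0.3 | 93.9% | 8.9 |
| 0.5 | 91.4% | 6.4 |
| 0.7 | 88.8% | 3.8 |

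**3. Direction under other mechanisms.** True sensitivity is 85% (section 8.2). True specificity is assumed to be 75%, inside the 53% to 96% that section 8.2 cites from glioma studies.

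- (a) A fraction f of discordant scores is moved to agree with location: the apparent value is s + (1−s)·f.
- (b) Fluorescent spots are r times as likely to be verified: sensitivity is rs/(rs + 1 − s) and specificity is c/(c + (1−c)r).
- (c) Clear-cut spots (bright in tumor, dark at margin) are r times as likely: sensitivity is as in (b) and specificity is rc/(rc + 1 − c).

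| Mechanism | Sensitivity | Specificity |
|---|---|---|
| (a) f = 0.1 to 0.5 | 86.5% to 92.5% | 77.5% to 87.5% |
| (b) r = 1.5 to 3 | 89.5% to 94.4% | 66.7% down to 50.0% |
| (c) r = 1.5 to 3 | 89.5% to 94.4% | 81.8% to 90.0% |

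Sensitivity rises under all three. Specificity rises under (a) and (c) and falls under (b), and section 4.4's text on specimens from fluorescent areas leaves room for (b).

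**4. Against the precision with several samples.** With 23 × 3 = 69 tumor samples at 85%, the simple half-width is 1.96·√(0.1275/69) = 8.4 points if samples are independent. At within-patient correlation 0.5 the design effect is 1 + 2·0.5 = 2 and the half-width is 11.9 points. Set against step 2 at the same correlation, the illustrative excess is 12.8/8.4 ≈ 1.5 half-widths at ρ = 0 and 6.4/11.9 ≈ 0.5 at ρ = 0.5.

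**5. Masking, side by side.** Section 4.4: the pathologist is one "a pathologist who will not be informed of the fluorescence status of the tissue samples". Section 8.2: the pathologists receive the marked specimen, and "Each region will be marked according to the associated intensity of the PPIX tissue fluorescence score at that location". If the mark shows the score, both statements cannot hold. If it does not, section 8.2 does not say how the score is linked to the region.

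**The case against.** The strongest defence is that this is an open-label feasibility pilot of a tool the operating surgeon will read in context. Knowing where the tumor lies is part of intended use, and section 8.2 assigns regions by location, not by brightness. Sites without fluorescence go through the same histology, so dark cases are not dropped. This stands as far as it goes: surgeon scoring is reasonable. But a location rule that fixes only the zone does not fix the spot, and keeping dark sites does not prevent selection within a specimen.

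Several stronger readings are tempting, and the documents do not support them.

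- A reader might infer that specificity is inflated too. Step 3 shows that its direction depends on the mechanism. The low cut-off at score 1 favours sensitivity at the expense of specificity, and it is a prespecified definition, not in itself a bias.
- A reader might infer that the surgeon's tumor or margin label sets the truth. It does not: under section 8.3 pathologists determine malignancy in each sample, so a dark margin spot containing tumor counts as a false negative.
- A reader might infer that the pathologist is certainly unmasked. Section 8.2 does not say that the score appears on the pathology label; the texts conflict, and that is all they show.

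**Conclusion.** The point holds. The surgeon, having seen the fluorescence and knowing the tumor location, chooses the exact regions for verification and assigns the subjective score, and nothing makes the spot within each zone independent of fluorescence. Sensitivity is likely to be biased upward; specificity may be biased in either direction.

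The documents do not allow the size to be estimated. The range of about 89% to 98% for a true 85% follows from one assumed rule (the brighter of two spots, every time) and correlations from 0.7 to 0. A reader might take the resulting 4 to 13 points as an expected bias; it is only an illustration of what the plan leaves open.

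The conflict between sections 4.4 and 8.2 on what the pathologist sees needs reconciling whatever the size of any bias.

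**What to change.** In sections 4.4 and 8.2:

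- State that the regions (three tumor, one boundary) are located by a fixed anatomical rule that does not depend on fluorescence, and are numbered under white light. Where interior tumor is not exposed beforehand, do this on the resected specimen. There the surgeon will already have seen blue light, so the fixed rule is what secures independence.
- Record the blue-light score for each numbered region on the CRF before any frozen or permanent histology result is known. The frozen result matters because section 4.4 sends all tumor specimens for frozen examination.
- Send specimens to pathology labelled with the region number only, and reword section 8.2 to agree with the masking in section 4.4.

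The cost is procedure wording, a CRF line and slightly more marking time, with no extra staff, tissue or patients. The sensitivity estimate may come out lower. The surgeon remains the scorer, as in intended use, so knowledge of tumor location at scoring should be reported as a remaining limitation.

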5.2.3 Within 48h after treatment termination

- · Physical exam, vital signs
- Monitoring for adverse effects

5.3 Follow-up Procedures

- **5.3.1** Patients will be followed at designated time points of within 48h, 2 weeks, and 6 weeks postoperatively for regular post-surgical examinations. Recorded at these visits:
 - Physical exam, vital signs
 - Concurrent medications
 - Adverse events

5.4 Time and Events Table

Study Assessment or Procedure	Baseline (-60 to day 0 before surgery)	Day 0 (At 5-ALA administr ation)	Day 0 (prior to surgery)	Within 48h of surgery	Week 2	Week 6
Informed Consent	X					
Demographics and Medical History	Х			X	Х	Х
Physical Exam (vitals, weight, Karnofsky status)	Х	X		X	Х	Х
Concurrent Medications	Х	Х	Х	Х	Х	Х
Adverse Events Evaluation	Х	Х	Х	Х	Х	Х
Tumor Imaging	Х					
Pregnancy test ^d	Х					
Other labs (CMP, CBC, GGT) ^{a,b,c}	Х			Х	Х	Х
Gleolan® (5- ALA) ^e		X				

- a. Albumin, alkaline phosphatase, total bilirubin, bicarbonate, BUN, calcium, chloride, creatinine, glucose, potassium, total protein, SCOT (AST), SCPT (ALT), sodium, gamma glutamyl transpeptidase (GGT)
- b. Phosphorus, uric acid, creatinine kinase, and amylase will be added as clinically necessary/indicated.
- c. Repeat only those labs that remain abnormal after 6 weeks unless attributed to other therapy
- d. Pregnancy test (women of childbearing potential)- part of standard pre-operative protocol
- e. Gleolan® (5-ALA) is dosed as 20mg/kg. Oral administration is one-time only and based on actual weight on day of surgery.

5.5 Removal of Subjects from Study

Patients can be taken off the study treatment and/or study at any time at their own request, or they may be withdrawn at the discretion of the investigator for safety, behavioral or administrative reasons. The reason(s) for discontinuation will be documented and may include:

- 5.5.1 Patient voluntarily withdraws from treatment (follow-up permitted);
- 5.5.2 Patient withdraws consent (termination of treatment and follow-up);

- 5.5.3 Patient is unable to comply with protocol requirements;
- 5.5.4 Patient demonstrates disease progression (unless continued treatment with study drug is deemed appropriate at the discretion of the investigator);
- 5.5.5 Patient experiences toxicity that makes continuation in the protocol unsafe;
- 5.5.6 Treating physician judges continuation on the study would not be in the patient's best interest:
- 5.5.7 Patient becomes pregnant (pregnancy to be reported along same timelines as a serious adverse event);
- 5.5.8 Development of second malignancy (except for basal cell carcinoma or squamous cell carcinoma of the skin) that requires treatment, which would interfere with this study;
- 5.5.9 Lost to follow-up. If a subject cannot be located to document status after a period of 2 months postoperatively, the subject will be considered lost to follow-up. All attempts to contact the subject during this time period will be documented.

6. ADVERSE EVENTS

6.1 Adverse Event Monitoring

Adverse event data collection and reporting, which are required as part of every clinical trial, are done to ensure the safety of Subjects enrolled in the studies as well as those who will enroll in future studies using similar agents. Adverse events are reported in a routine manner at scheduled times during a trial. Additionally, certain adverse events must be reported in an expedited manner to allow for optimal monitoring of patient safety and care.

All patients experiencing an adverse event, regardless of its relationship to study drug, will be monitored until:

- the adverse event resolves or the symptoms or signs that constitute the adverse event return to baseline;
- any abnormal laboratory values have returned to baseline;
- there is a satisfactory explanation other than the study drug for the changes observed; or
- death.

6.2 Definitions

6.2.1 Definition of Adverse Event

An adverse event (AE) is any untoward medical occurrence in a patient receiving study treatment and which does not necessarily have a causal relationship with this treatment. An AE can therefore be any unfavorable and unintended sign (including an abnormal laboratory finding), symptom, or disease temporally associated with the use of an experimental intervention, whether or not related to the intervention. The occurrence of an AE may come to the attention of study personnel during study visits and interviews or by a study participant presenting for medical care. Adverse events will be coded in accordance with the CTCAE V4.0. For analysis of adverse events, AEs will be obtained at the time of ingestion of the investigational product before surgery, during the first 48 hours, 2 weeks and 6 weeks after surgery. In addition, serious adverse events (SAE) will be collected beginning from the time the subject signs consent. All AEs must be

graded for intensity and relationship to study product. The investigator is responsible for recording all AEs that are observed during this study according to the definition.

6.2.2 Severity of Adverse Events

If possible, all AE will be graded according to the NCI Common Terminology Criteria for Adverse Events (CTCAE) version 4.0. The CTCAE v4 is available at http://ctep.cancer.gov/reporting/ctc.html

If no CTCAE grading is available, the severity of an AE is graded as follows:

Mild (grade 1): the event causes discomfort without disruption of normal daily activities.

Moderate (grade 2): the event causes discomfort that affects normal daily activities.

Severe (grade 3): the event makes the patient unable to perform normal daily activities or significantly affects his/her clinical status.

Life-threatening (grade 4): the patient was at risk of death at the time of the event.

Fatal (grade 5): the event caused death.

6.2.3 Serious Adverse Events

A "serious" adverse event is defined in regulatory terminology as any untoward medical occurrence that:

6.2.3.1 Results in death.

If death results from (progression of) the disease, the disease should be reported as event (SAE) itself.

6.2.3.2 Is life-threatening.

(the patient was at risk of death at the time of the event; it does not refer to an event that hypothetically might have caused death if it were more severe).

- **6.2.3.3** Requires in-patient hospitalization or prolongation of existing hospitalization for \geq 24 hours.
- **6.2.3.4** Results in persistent or significant disability or incapacity.
- **6.2.3.5** Is a congenital anomaly/birth defect

